11.2.2 Primary Analysis of Secondary Endpoints

Unless otherwise specified, the primary analysis for the secondary endpoints will be analyzed using MMRM described in 11.1.2.1 based on the FAS for U.S., and PPS for non-inferiority tests and FAS for superiority tests for Ex-U.S. if applicable.

11.2.2.1 Proportion of Hemoglobin Responders

- US: Proportion of subjects with mean hemoglobin level during the evaluation period defined as Week 28 until Week 52 ≥ 10.0 g/dL, and patients with mean hemoglobin level between Hb 10-12 g/dL.
- Ex-US: Proportion of subjects with mean Hb between range of 10.0 to 12.0 g/dL without having received rescue therapy within 6 weeks prior to and during this 8-week evaluation period.

The hypothesis to be tested for the efficacy analysis is:

H0: Hemoglobin response rate for subjects in the roxadustat group - hemoglobin responder rate for subjects in the Epoetin group $\leq -15\%$

Versus

H1: Hemoglobin response rate for subjects in the roxadustat group - hemoglobin responder rate for subjects in the Epoetin group $> -15\%$.

A 2-sided 95% confidence interval for the difference of 2 responder rates (roxadustat – ESA) based on the Miettinen & Nurminen approach adjusting for treatment group and stratification factors will be calculated and non-inferiority will be declared if the lower bound of the 95% CI is greater than -15%.

Subjects who dropped out from the study before week 28 will be treated as non-responder.

11.2.2.2 Change from Baseline in LDL Cholesterol Averaged over Weeks 12 to 28

The change from baseline in LDL cholesterol will be analyzed and compared between the 2 treatment groups using MMRM model with baseline LDL cholesterol as a covariate and treatment group, visit, the interaction of treatment and visit, and the above mentioned stratification factors as fixed effects. The same strategy as that used in MMRM for Hb will be used to choose variance covariance structure. Data up to visit of Week 52 will be included in the model. The estimates for difference of LDL Cholesterol averaged over Weeks 12 to 28 between the two treatments groups will be generated from an estimate statement from Visit Week 12 to 28. Superiority will be declared if the upper bound of the 2-sided 95% confidence interval of the difference between roxadustat and active control does not exceed 0.

Baseline, LDL, is defined as the last available value obtained prior to the first dose of study drug.

11.2.2.3 Hemoglobin change from baseline to the average level during the Week 18 to 24 for Subjects with CRP > ULN

Change from baseline in Hemoglobin from baseline to the average level during the Week 18 to 24 will be analyzed using the ANCOVA MI as the primary endpoints. Both Non-inferiority of roxadustat vs. Epoetin and superiority will be tested. The non-inferiority margin is fixed as a difference of -0.75.

11.2.2.4 Average Monthly of IV Iron Use during Weeks 28 to 52.

The average monthly IV iron use during Weeks 28 to 52 Treatment Period will be calculated for monthly intervals. The Treatment Period will be divided in periods of 28 days and for each of these periods the monthly mean of IV iron will be calculated using the following formula:

Monthly iron use for each subject = Total IV iron in mg / [(last visit date – first dose date of study medication +1)/ 28]

The average monthly iron use will be compared between the 2 treatment groups using An ANCOVA model with baseline iron repletion status, treatment group, and stratification factors as fixed effects. Superiority will be declared if the lower bound of the 2-sided 95% confidence interval of the difference between active control and roxadustat exceeds 0.

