4.2 Secondary Efficacy Endpoints

The secondary efficacy endpoints in this study are as below for both US and Ex-US submission unless otherwise specified:

- US (FDA) submission: Proportion of subjects with mean hemoglobin level during the evaluation period defined as Week 28 until Week 52 ≥ 10.0 g/dL.
- Ex-US submission: Proportion of subjects with hemoglobin response, defined as mean hemoglobin during Weeks 28 to 36 within the target range of 10.0 to 12.0 g/dL without having received rescue therapy within 6 weeks prior to and during this 8-week evaluation period.
- Change from baseline in Low Density Lipoprotein (LDL) cholesterol to the average LDL cholesterol of weeks 12 to 28.
- Hemoglobin change from baseline to the average level during the Weeks 18 to 24 for subjects with baseline hs-CRP $>$ ULN.
- Average monthly IV iron use per subject during the Treatment Period during Weeks 28 to 52 (monthly defined as a period of 4 weeks).
- Time to first RBC Transfusion during the treatment
- Change from BL in mean arterial pressure (MAP) to the MAP value averaged over weeks 20 to 28
- Time to first exacerbation of hypertension: An increase from BL of ≥ 20 mm systolic blood pressure (SBP) and SBP ≥ 170 mmHg or an increase from baseline of ≥ 15 mmHg diastolic blood pressure (DBP) and DBP ≥ 100 mmHg during Weeks 28 to 52.

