4.3 Additional Evaluation of Efficacy

The additional efficacy evaluations in this study are:

- **Hemoglobin Maintenance:**
 - Hemoglobin long-term Maintenance: Mean change from baseline in hemoglobin averaged over 8 weeks of treatment at Weeks 44-52 without

- rescue therapy within 6 weeks prior to and during this 8-week evaluation period.
- Mean change from baseline in hemoglobin averaged over the Week 96 to 104 of treatment, without rescue therapy within 6 weeks prior to and during this 8-week evaluation period.
 - Change from baseline in hemoglobin at each of the selected post-dosing time points.
 - Proportion of subjects with Hb ≥ 10 g/dL averaged over Weeks 28 to 36, 44 to 52, and 96 to 104 of treatment without rescue therapy within 6 weeks prior to and during the evaluation periods.
 - Proportion of subjects with Hb ≥ 10 g/dL averaged over Weeks 28 to 36, 44 to 52, and 96 to 104 of treatment regardless of rescue therapy
 - Proportion of subjects with Hb within 10-12 g/dL averaged over Weeks 28 to 36, 44 to 52, and 96 to 104 of treatment without rescue therapy within 6 weeks prior to and during these 8-week evaluation periods.
 - Proportion of subjects with Hb within 10-12 g/dL averaged over Weeks 28 to 36, 44 to 52, and 96 to 104 of treatment regardless of rescue therapy use.
 - Hemoglobin change from baseline to the average hemoglobin value of weeks 28 to 36, 44 to 52, and 96 to 104 of treatment regardless of the use of rescue therapy.
- **Iron Supplement:**
 - Time to and Proportion of subjects who has requirement for IV iron supplementation.
 - Mean monthly IV iron (mg) per subject during weeks 28-52, 53-104, and 105 -EOT.
 - Mean monthly oral iron (mg) use per subject during 28-52, 53-104, and 105 - EOT.
 - Proportion of subjects who has Requirement for only oral iron supplementation (Week 1 to 52).
 - **Hospitalizations**
 - Time to first hospitalization (% of subjects) up to Week 52, 7 days after Last Dose. Time to first hospitalization or skilled nursing facility (% of subjects) up to Week 52, 7 days after Last Dose.
 - Number of days of hospitalizations due to AE per subject-exposure year (PEY)
 - Number of days in hospital or skilled nursing facility due to AE per patient-year exposure (PEY)
 - Number of days in medical-facility (hospital, skilled nursing facility, emergency room, or overnight observation) due to AE per patient-year exposure (PEY)

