11.2 Analysis of Secondary Endpoints

11.2.1 Secondary Endpoints and Hypothesis Testing

Once the null hypothesis of the primary endpoint has been rejected, the secondary endpoints below will be tested using a fixed sequence testing procedure, in order to maintain the overall two-sided type I error of 0.05. If the claim of superiority or non-inferiority is successful and the test will progress to the next comparison in sequence as follows.

Table 6 Key Secondary Endpoints Fixed Sequence Testing Procedure

Test	Variable	Comparison
1	Proportion of subjects with mean hemoglobin level during the evaluation period defined as Week 28 until Week 52 \geq 10.0 g/dL (U.S.) or Proportion of Hb responders in the average of weeks 28 to 36 within the target range of 10.0 to 12.0 g/dL without having received rescue therapy. (Ex-U.S.).	Non-inferiority of roxadustat versus EPO with margin of -0.15
2	LDL cholesterol change from BL to the average of weeks 12 to 28.	Superiority of roxadustat versus EPO
3	Hemoglobin change from baseline to the average level during Weeks 18 to 24 for subjects with baseline hsCRP > ULN	Non-inferiority of roxadustat versus EPO
4	Average monthly IV iron (mg) use per subject during weeks 28 to 52.	Superiority of roxadustat versus EPO
5	Time to first RBC Transfusion during the treatment.	Non-inferiority of roxadustat versus Epo with margin of 1.8
6	MAP change from BL to the average MAP of weeks 20 to 28.	Superiority of roxadustat versus EPO
7	Time to first exacerbation of hypertension: An increase from baseline of \geq 20 mmHg systolic blood pressure (SBP) and SBP \geq 170 mmHg or an increase from baseline of \geq 15 mmHg diastolic blood pressure (DBP) and DBP \geq 100 mmHg during Weeks 28 to 52.	Superiority and Non-inferiority of roxadustat versus EPO with margin of 1.8

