11.3.3.3 Use of Iron

IV Iron

Only IV iron therapy that started during the study treatment and up to the ET/EOT Visit will be taken into account for the total amount.

The average monthly IV iron use during weeks 53 to EOS will be calculated for monthly intervals. The Treatment Period will be divided in periods of 28 days and for each of these periods the monthly mean of IV iron will be used using the following formula:

Monthly iron use for each subject = $\text{Total IV iron in mg} / [(\text{last visit date} - \text{first dose date of study medication in the period} + 1) / 28]$

The following 2 endpoints will be analyzed:

- Proportion of subjects who receive IV iron. The proportion of subjects who received IV iron will be compared between the 2 treatments using logistic regression model adjusting for baseline iron repletion status and treatment group and stratification factors as fixed effects. (This will be performed for week 1 to week 36 as well).
- The average monthly iron use will be compared between the 2 treatment groups using ANCOVA model with baseline iron repletion status, and treatment group, and stratification factors as fixed effects.

Oral iron

The average monthly oral iron use during Weeks 28 to 52, and weeks 53 to ET/EOT will be calculated similarly to IV iron for monthly intervals.

The following 2 endpoints will be analyzed:

- Proportion of subjects who receive Oral iron. The proportion of subjects who received oral iron will be compared between the 2 treatment groups using logistic regression model adjusting for baseline iron repletion status, treatment group and stratification factors as fixed effects.
- The average monthly oral iron use will be compared between the 2 treatment groups using ANCOVA model with baseline iron repletion status, treatment group, and stratification factors as fixed effects.

In addition the proportion of subjects who received both IV and/or oral iron will be compared between the 2 treatments using logistic regression model adjusting for baseline iron repletion status and treatment group and stratification factors as fixed effects.

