16.5 Appendix 5 Data Handling Conventions

16.5.1 Visit Time Windows

The table below presents the visits assigned for efficacy and safety analyses corresponding to the range of treatment days (window) during which an actual visit may have occurred.

Table 11. Visit Time Windows

Derived Visit	Scheduled Visit Day ^a	Window
Baseline, Week 0	Day 1	Days ≤ 1
Week 1	Day 7*(Week #)+1	Days [Day 2, 10]
Week 2	Day 7*(Week #)+1	Days [Scheduled Day ± 3 Scheduled Day ± 6]
Weeks 4 prior to 24	Day 7*(Week #)+1	Days [Scheduled Day ± 7 , Scheduled Day ± 6]
Week 24	Day 7*(Week #)+1	Days [Scheduled Day ± 7 Scheduled Day ± 13]
\geq Week 28	Day 7*(Week #)+1	Days [Scheduled Day ± 14 , Scheduled Day ± 13]
ET	Earlier Termination, match to a closest scheduled visit in protocol if patient had not been off drug for more than 7 days.	
EoT	Last assessment between Day 2 and EOT visit day, match to a closest scheduled visit in protocol if patient had not been off drug for more than 7 days.	
EoS (FU-4Wk)	Final visit for the Study 15 – 31 days after the last dose (excluding long term follow-up for early termination).	

^a: Relative to the first study medication date. For example, Day 1 = the first dose date of study medication.

Table 12: Analysis Visit Windows for QoL

CRF Visit	Target Day ^a	Analysis Visit Windows Actual Assessment Day	Analysis Visit
Day 1	Day 1	Day 1	Baseline
Week 12	Day 7 * (Week #) + 1	Target day -14, Target Day + 27	Week 12
Week 28	Day 7 * (Week #) + 1	Target Day – 28, Target Day +83	Week 28
Week 52	Day 7 * (Week #) + 1	Target Day – 84, Target Day + 83	Week 52
EOT Visit		Last assessment between Day 2 and EOT visit day, remapped to the closest next scheduled visit for HRQoL collection.	Week 12, 28, 52 and > 1 year

^a: Relative to Day 1 (first dose date of study medication)

Table 13. Analysis Visit Windows for Lipid Panel

Derived Visit	Scheduled Visit Day ^a	Window
Baseline, Week 0	Day 1	Day 1
Week 4	Day 7*(Week #)+1	[Day 2, Day +42]
Week 8	Day 7*(Week #)+1	[Scheduled Day-14, Scheduled Day +13]
Weeks 12	Day 7*(Week #)+1	[Scheduled Day -14, Scheduled Day +27]
Week 20, 28	Day 7*(Week #)+1	[Scheduled Day -28, Scheduled Day +27]
Weeks 36	Day 7*(Week #)+1	[Scheduled Day -28, Scheduled Day +41]
Week 48 to xx	Day 7*(Week #)+1	[Scheduled Day -42, Scheduled Day +41]
Week xx	.	Last assessment between Day 2 and EOT visit day, match to a closest scheduled visit in protocol if patient had not been off drug for more than 7 days

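### The formula for monthly IV iron (test 4 of the fixed sequence) is not limited to Weeks 28 to 52; as written it averages over the whole time from first dose

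*SAP*

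**What the plan says.** The declared endpoint is clear. SAP 4.2 lists average monthly IV iron "during the Treatment Period during Weeks 28 to 52 (monthly defined as a period of 4 weeks"). Table 6 in SAP 11.2.1 gives test 4 as "Average monthly IV iron (mg) use per subject during weeks 28 to 52", tested for superiority. The heading of SAP 11.2.2.4 names the same weeks, and its lead-in says: "The average monthly IV iron use during Weeks 28 to 52 Treatment Period will be calculated for monthly intervals".

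The lead-in then cuts the Treatment Period into 28-day periods and gives one formula for each subject: "Total IV iron in mg / [(last visit date – first dose date of study medication +1)/ 28", with a closing bracket. Superiority requires the lower 95% confidence limit for control minus roxadustat, from an ANCOVA, to lie above 0.

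Three other places bear on it:

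- SAP 11.3.3.3 has the only rule on which iron counts: IV iron started on study treatment and "up to the ET/EOT Visit will be taken into account for the total amount". Its own formula, for the period from Week 53, is nearly the same but starts the clock at the "first dose date of study medication in the period".
- SAP 4.3 asks for "Mean monthly IV iron (mg) per subject during weeks 28-52, 53-104, and 105 -EOT".
- Protocol 3.2.2 defines the corresponding secondary endpoint over Weeks 1 to 36, a window that does start near first dose.

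**The concern.** Test 4 carries alpha and gates tests 5 to 7. It also serves the secondary objective on IV iron utilization. Its formula has no term for the window. The total is unqualified, and the time starts at first dose and ends at the last visit. The reference to 28-day periods does not help, because nothing in the formula changes from one period to the next and every period would return the same number.

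The result equals the declared endpoint only if a subject's average rate outside Weeks 28 to 52 equals the rate inside it. Treatment duration varies, up to about 3 years after the last subject is randomized (SAP 3), so the share of time from outside the window also varies between subjects. If use changes over time and discontinuation differs by arm, the two arms are averaged over different mixes of early and late use, and the superiority test can err either way.

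Two gaps are linked to this:

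1. The last visit date is not defined in 11.2.2.4. SAP Table 11 describes the EOS visit as the "Final visit for the Study 15 – 31 days after the last dose (excluding long term follow-up for early termination"). If that is what is meant, the time runs about 4 weeks past the point at which iron stops being counted.
2. The analysis uses the FAS, which needs only one dose and one post-dose Hb. No rule covers FAS subjects with no treatment time in the window. Followed literally, they enter with a value made up entirely of iron given outside it. SAP 11.2.2.1 has a rule for dropout before Week 28 in test 1; test 4 has none.

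**Working it through.** The documents give no sample size, SD or expected difference for IV iron, so there is no stated figure to reproduce. The check evaluates the formula as printed.

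**Window.** SAP Table 11 dates week w at Day 7w + 1. Week 28 is 7×28 + 1 = Day 197 and Week 52 is 7×52 + 1 = Day 365. The window is 365 − 197 + 1 = 169 days, or 169/28 = 6.04 four-week months.

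**Share of averaged time outside the window**, 1 − 169/L, where L is the day of the last visit:

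| Last visit | L | Outside the window |
|---|---|---|
| Week 52 | 365 | 53.7% |
| Week 104 | 729 | 76.8% |
| Week 156 | 1093 | 84.5% |

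**Effect on one subject's value.** Assume the rate before Week 28 is k times a constant later rate. Then literal value / declared value = (196k + L − 196)/L.

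| Last visit | k = 2 | k = 0.5 | k = 1 |
|---|---|---|---|
| Week 52 | 561/365 = 1.54 | 267/365 = 0.73 | 1.00 |
| Week 104 | 925/729 = 1.27 | 631/729 = 0.87 | 1.00 |
| Week 156 | 1289/1093 = 1.18 | 995/1093 = 0.91 | 1.00 |

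**Window on the total only.** Reading the window into the total but not the time is worse. Constant use is then understated 365/169 = 2.16, 729/169 = 4.31 or 1093/169 = 6.47-fold. This is not the literal reading; it shows that both terms have to be limited together.

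**EOS as end date.** Take EOS at 28 days after end of treatment (Protocol 7.2.1 sets it at 4 weeks). Constant use is understated by 1 − 365/393 = 7.1% if treatment ends at Week 52, and by 1 − 57/85 = 32.9% if it ends at Week 8.

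**Effect on the test (illustration).** Every input here is an assumption except the 300 and 600 per arm, which follow from the planned 600 to 1200 subjects. Iron rates have the same distribution in both arms: normal with mean 90 and SD 110 mg per 28 days, floored at 0 (mean about 103). Administrative follow-up is uniform over 52 to 156 weeks and discontinuation is exponential. The comparison is an unadjusted two-sample 95% confidence interval, with 4,000 replicates. Each cell gives false superiority / error against roxadustat; 2.5% each is nominal. Unless stated otherwise, 20% of the roxadustat arm and 30% of the epoetin arm stop by Week 52, which means 1 − 0.8^(28/52) = 11.3% and 1 − 0.7^(28/52) = 17.5% stop before Week 28.

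| Scenario | 300 per arm | 600 per arm |
|---|---|---|
| Literal, k = 2 | 8.6% / 0.5% | 13.2% / 0.2% |
| Literal, k = 0.5 | 0.6% / 8.4% | 0.1% / 12.4% |
| Literal, k = 2, stopping rates swapped | 0.7% / 8.1% | 0.2% / 13.4% |
| Constant use, end date = EOS | 1.1% / 4.9% | 1.0% / 5.7% |

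With constant use and end of treatment as the end date, the literal formula gives 2.2 to 2.9%. With equal 20% stopping and k = 2 or 0.5 it gives 2.3 to 2.8%. The formula limited to the window, in subjects with at least 7 days there, gives 2.1 to 3.2% in every scenario.

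**The case against.** The strongest reply is that this is a drafting slip. The window is stated four times, the lead-in says the calculation is done by 28-day period, and the near-identical formula in 11.3.3.3 suggests that a few words were dropped. A careful programmer would query it, and table specifications sit in a separate document that was not available for this review. That is fair as to intent, which is not in doubt. But the SAP is where the rule is fixed, this rule gives a different quantity, and in an open-label trial the choice should not be left to programming.

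Second, the error rates rest on large assumed inputs: a two-fold change in use together with a 10-point gap in discontinuation. Milder inputs give less: 1.25-fold early use with 20% vs 30% stopping, or doubled use with 20% vs 25%, puts false superiority at about 4 to 6%. The planned ANCOVA, with iron repletion status and stratification factors, was not simulated. This stands, and the simulation should be read only as showing that the error can occur in both directions.

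Third, the EOS reading is the unfavourable one: the lead-in speaks of the Treatment Period, and SAP 16.5.1 elsewhere refers to the last visit within it. That is also fair. The percentages apply only if EOS is meant; the term still needs a definition.

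Fourth, the separate periods in SAP 4.3 belong under 11.3.3.3, whose formula does limit its start date. That formula leaves its total and end date unrestricted, so it needs the same correction.

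Fifth, a windowed rate is unstable for subjects with very little time in the window: 100 mg with one day there scores 100/(1/28) = 2,800 mg per month. This is a valid caution, taken up in the fix.

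**Conclusion.** The concern holds. The formula for an alpha-controlled superiority test does not compute the declared endpoint, and it must be corrected before the analysis is programmed. That 53.7% to 84.5% of the averaged time falls outside Weeks 28 to 52, for last visits from Week 52 to Week 156, follows from the SAP's own day rule and needs no assumption about iron use.

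How far a value moves does depend on the pattern of use: 0.73 to 1.54 times the declared value for a two-fold change either way at Week 28, and no change if use is constant. With end of treatment as the end date, the test is distorted in these scenarios only when use changes over time and discontinuation also differs by arm. The documents report neither, so no direction or actual size of bias can be stated. If the end date is EOS, unequal discontinuation alone is enough. That the formula was carried over from the Protocol's Weeks 1 to 36 endpoint is plausible, but it is an inference.

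**What to change.** In SAP 11.2.2.4, replace the formula with: IV iron in mg given from Day 197 to the earlier of Day 365 and end of treatment, divided by (on-treatment days in that same interval / 28). Replace the last visit date with end of treatment.

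State the rule for FAS subjects with no treatment time in the window, and set a minimum time in it so that a day or two cannot produce an extreme monthly rate. The illustration used at least 7 days; the sponsor should choose and justify its own value. Excluding such subjects makes the comparison one among those still on treatment at Week 28, and the SAP should say so.

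In SAP 11.3.3.3, limit both the total and the time to the stated period, so that the Weeks 53 to 104 and 105 to EOT values in SAP 4.3 can be produced.

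The cost is one formula and its near-copy, one end-date definition, and a sentence or two on subjects with little or no time in the window. No new data are needed.

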11.2.2.5 Time to first RBC Transfusion

Time to the first RBC transfusion during treatment will be analyzed and compared between the 2 treatment groups using the Cox Proportional Hazards model adjusting for baseline Hb, treatment group and stratification factors.

Non-inferiority of roxadustat vs. Epoetin will be declared if the upper bound of the 2-sided 95% confidence interval of the hazard ratio is less than 1.8 and superiority.

11.2.2.6 Mean change in pre-dialysis mean arterial pressure (MAP) averaged over Weeks 20-28

Mean Arterial Pressure (MAP) will be calculated for each subject using the following formula:

$$\text{MAP} = (2/3) * \text{DBP} + (1/3) \text{SBP}.$$

Mean change from baseline in MAP will be analyzed and compared between the 2 treatment groups using an MMRM model with baseline MAP as a covariate, treatment group, visit, the interaction of treatment and visit, and stratification factors as fixed effects. The same strategy as that used in MMRM for Hb will be used to choose variance covariance Structure. Data up to visit of Week 52 will be included in the analyses. The estimates for difference of mean change from baseline in MAP for Week 20 to 28 between two treatment groups will be generated from an estimate statement. Superiority will be declared if the upper bound of the 2-sided 95% confidence interval of the difference between roxadustat and Epoetin (roxadustat – Epoetin) is below 0.

